### 12.2 Examination and approval of clinical trial protocol

The clinical investigation plan and Patient Informed Consent form used to study the SAPIEN 3 THV System must be reviewed and approved by the appropriate national authority and local or regional Ethics Committee (EC) where the clinical investigation is to be conducted before

enrolment of patients may begin. Any additional requirements imposed by the EC or regulatory authority shall be followed.

Changes to the investigational plan that may increase the risk or present new risks to the patient must be approved in writing by Edwards Lifesciences and the EC before the change is implemented.

### 12.3 Informed consent process and text of informed consent

The Patient Informed Consent Form must be approved by Edwards Lifesciences and the site's EC.

The study investigator(s) and support staff will approach patients with symptomatic aortic stenosis to assess their interest in participating in the study. They will provide an overview of the study and device, including the background, benefits, risks, and study procedures. If patients are interested in participating in the study, then they will be provided with the full Patient Informed Consent Form document. Patients will be allowed to read the document in its entirety, and then delegated study personnel will answer all of their questions. If the patient is comfortable with proceeding, then they will be asked to sign and date the Patient Informed Consent Form. Informed consent must be obtained prior to the screening procedures or baseline tests that are specific to this study.

During the course of the study, if new information becomes available that can affect a patient's future health and medical care, then the information will be provided to the patient and the process documented. If relevant, all affected patients will be asked to confirm their continuing informed consent in writing.

All patients who sign a Patient Informed Consent Form should be entered in the database. Data should not be entered until a Patient Informed Consent Form is signed. Patients that are screened and do not sign a Patient Informed Consent Form should be documented on the Screening Log.

## 13. Provisions on adverse event and device defect report

### 13.1 Adverse events

Adverse events may be volunteered by patients, elicited from questioning by Investigator or delegated study personnel, or collected via observation by the Investigator. In addition, patients will be instructed to contact the investigator, and/or study coordinator if any significant adverse events (e.g., expanded safety composite events) occur between study evaluation visits.

All adverse events are reported from the start of the procedure, which is defined as when anesthesia is first administered, and are reported until subject participation has ended (i.e. completion of the study or withdrawal of consent). Adverse events must be reviewed at every follow-up visit until resolution, AE has stabilized (according to Investigator), or the study has been completed. Should the adverse event be ongoing at time of study completion, the database should be updated to reflect status.

Reporting guidelines for adverse events:

- Record the number of units of blood needed for any transfusion associated with any overt bleeding event

- Failure of a percutaneous closure device shall be reported as an access site vascular closure device complication
- Vascular complications shall be designated as access or non-access related;

### 13.2 Serious Adverse Events

All Serious Adverse Events (SAE) and Unanticipated Serious Adverse Device Effect (USADE) must be reported to Edwards Lifesciences within 24 hours of the Investigator or delegated study personnel becoming aware of the event or according to local regulations (whatever is most stringent). SAEs and USADEs will be reported to the EC and regulatory authorities as required by national regulations or by the EC itself.

Information may be entered into the Case Report Form or reported directly to the Edwards Lifesciences, with documentation of such notification being recorded and filed. Notifications and source documents will be provided to Safety Officer.

At the time of initial notification, the following minimal information should be provided:

- Identifiable patient: subject number
- Identifiable reporter: study site
- Adverse event summary
- Causal relationship to device and procedure
- Awareness date

The USADE Case Report Forms should be completed within five working days. All USADEs must be followed until resolution or until a stable clinical endpoint is reached. All required treatments and outcomes of the USADE must be recorded.

Edwards will notify all participating clinical Investigators, ECs, and regulatory bodies as necessary of all USADEs that occur during the study within the specified reporting time frame following event notification. Investigators are responsible for reviewing information received about USADEs.

### 13.3 Reporting procedure and information of contact

#### Source Documents

The site will provide to Edwards Lifesciences a copy of anonymized supporting documentation (such as hospital record, laboratory results, autopsy results) of all SAEs and safety related composite events.

#### Investigator Assessment Responsibilities

The Investigator will determine if an adverse event is serious and not related, possibly related, or related to the device or procedure.

Pre-existing medical conditions or symptoms reported prior enrolment will be recorded in medical history form and will not be recorded as an adverse event. In the event there is a worsening in the pre-existing medical condition or symptoms after enrolment, then an adverse event will be recorded.

#### Sponsor Assessment Responsibilities

All adverse events will be reviewed by the Study Safety Officer who will determine if the adverse event is serious; anticipated or unanticipated; and not related, possibly related, or related to the device or procedure.

### Medical Reviewer Responsibilities

All endpoint related adverse events will be reviewed by a Medical Reviewer who will determine if the adverse event is serious; and not related, possibly related, or related to the device or procedure.

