### 7.1.3 Measures for reducing and avoiding bias

An independent Echocardiography Core Lab will be established for standardizing echocardiographic secondary endpoints. A Medical Reviewer will review all endpoint-related adverse events independently.

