## 7.3 Monitoring Plan

Edwards Lifesciences will contract with a Contract Research Organization (CRO) to provide a Clinical Research Associate(s) (CRA) to monitor the study sites to ensure that all investigators are in compliance with the protocol and the Investigator's Agreement, and that all study subjects have been properly consented with the current version of the informed consent document. Edwards Lifesciences will evaluate circumstances where an investigator deviates from the clinical protocol and will retain the right to remove either the investigator or the investigational site from the study.

Routine on-site monitoring visits shall include verification of the following:

- Compliance with the protocol, any subsequent amendment(s), GCP and maintenance of regulatory and EC requirements. Deviations shall be discussed with the Investigator(s) or delegated personnel, documented and reported
- Only authorized and delegated individuals are participating in the study
- The SAPIEN 3 THV System is being used according to the protocol and IFU
- Study Site resources, equipment and study personnel, remain adequate throughout the duration of the study
- Patient Informed Consent is completed in accordance to the protocol and regulations
- Only Patient Informed Consents Forms approved by the EC are used appropriately
- Source documents and other clinical records are accurate, complete up to date, stored and maintained properly
- CRFs and queries are complete, recorded in a timely manner, and consistent with source documents
- All adverse events and device deficiencies are reported to Edwards without unjustified delay
- All serious adverse events and deviations are reported to the EC, if required

- All other required reports, notifications, applications, submissions and correspondence are maintained in the investigator's files and are accurate, complete, timely, legible, dated and identify the clinical investigation
- Current laboratory normal values, laboratory certifications, accreditations, or other validations are present in the investigator's file
- Subject withdrawal has been documented; the monitor shall discuss this with the principal investigator or his/her authorized designee
- Subject non-compliance with the requirements stated in the informed consent has been documented; the monitor shall discuss this with the principal investigator or his/her authorized designee

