## **9. Data Management**

### **9.1 Data Collection**

Data will be captured and managed through an electronic data capture (EDC) system. Passwords will be issued to appropriate data management personnel to ensure confidentiality and protection of the data by allowing variable levels of access to the computer system.

Electronic CRFs (eCRFs) will be used to collect all patient data during the trial. eCRFs must be fully completed for each patient, and signed electronically by the investigator and/or designee.

The investigator, or an individual designated by him/her, is responsible for recording all data from the trial onto the eCRFs on a dedicated website. The investigator is required to provide an electronic signature on the appropriate eCRF pages to verify that he/she has reviewed the recorded data.

Completed eCRFs will be reviewed at the investigational site and remotely by authorized Edwards Lifesciences personnel at regular intervals throughout the trial. All eCRFs will be tracked at Edwards Lifesciences and missing or unclear data will be requested as necessary throughout the trial.

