### Medical Reviewers

Medical Reviewers will review and classify adverse events in accordance with the study protocol.

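### Medical review starts from reported adverse events, and no described step screens the collected labs, ECGs, neurological scales or other core-lab findings for unreported endpoint events, so event-based secondary rates may be under-counted

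*Combined protocol and SAP*

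**What the plan says.** Section 7.1.3 names two measures against bias: an independent echocardiography core laboratory and the Medical Reviewer. Of the second it says: "A Medical Reviewer will review all endpoint-related adverse events independently".

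Section 13.1 describes how an event enters the data: "Adverse events may be volunteered by patients, elicited from questioning by Investigator or delegated study personnel, or collected via observation by the Investigator".

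Section 13.3 then assigns three overlapping assessments. The investigator judges seriousness and relatedness. For the sponsor, "All adverse events will be reviewed by the Study Safety Officer who will determine if the adverse event is serious", together with whether it was anticipated and whether it was related. For the third, "All endpoint related adverse events will be reviewed by a Medical Reviewer who will determine if the adverse event is serious", together with relatedness. Section 20 widens the last role slightly: "Medical Reviewers will review and classify adverse events in accordance with the study protocol". No order of precedence is given if the three disagree. Under Source Documents in 13.3, sites send supporting records for serious adverse events and safety-related composite events.

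The visit schedule in 7.1.5.2 collects data that bear on the endpoints whether or not an event is reported. Creatinine, hemoglobin, ECG, NIHSS and mRS are taken at baseline, post-procedure, discharge and 30 days. CK/CK-MB and/or troponins are drawn at baseline, three times after the procedure, and at 30 days.

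**The concern.** Many secondary safety endpoints in 7.1.6 can leave a trace in scheduled measurements: stage II-III kidney injury in creatinine, infarction in cardiac markers, bleeding in hemoglobin, conduction disturbance on ECG, and stroke in NIHSS or mRS. Valve thrombosis and mitral apparatus damage may show on echo. Whether such a trace becomes a counted event depends first on someone reporting it. This is a single-arm trial, so every investigator knows the device was used and no control arm shares any under-reporting.

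A review that begins with reported events can correct how they are classified, but has no described means of finding an unreported one. At stake are the descriptive complication rates that form part of the safety evidence for Chinese regulatory approval (section 3.1).

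**Working it through.** **The plan's own figure.** The only derived number in section 8 is the drop-out rate in 8.3: (60 − 50)/60 = 16.7%, which agrees with the stated bound of under 17%. The present point does not depend on it; it supplies only the range n = 50 to 60. The As Treated population could slightly exceed 60, because 7.1.5.1 counts toward the 60 only patients who leave the procedure room with the valve in place.

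**Step 1: does any described step find an unreported event from collected values?**

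| Step | Starts from | Compares values with endpoint definitions? |
|---|---|---|
| Event collection (13.1) | Patient report, questioning, investigator observation | Not stated |
| Safety Officer (13.3) | Adverse events | Not stated |
| Medical Reviewer (7.1.3, 13.3, 20) | Endpoint-related or recorded adverse events | Not stated |
| On-site monitoring (7.3) | Event reporting and CRF agreement with source | Not stated |
| Remote eCRF review (9.1) | Missing or unclear entries | Not stated |
| Document requests (15) | A right the sponsor reserves | No trigger stated |
| Core laboratory (7.1.6, 8.4) | All 30-day echoes, for stenosis and regurgitation | Not needed for these endpoints; no route stated for other findings |

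Take a creatinine rise that is correctly transcribed but not reported as an event. It agrees with source and is neither missing nor unclear, so it could pass the checks in 7.3 and 9.1 as they are described.

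**Step 2: weight of one missed event.** The change in a rate is 1/n: 1/60 = 1.7 points and 1/50 = 2.0 points. For scale, the exact (Clopper-Pearson) 95% interval is 0.49% to 13.71% for 2/50 = 4.0%, and 1.25% to 16.55% for 3/50 = 6.0%. One event is small against the width of the interval. The interval describes sampling error, however, and does not allow for events that were never counted.

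**Step 3: illustration under assumptions.** Let p be the true event rate and s the share of true events that are reported. The documents give neither.

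- Expected reported rate = p × s
- Expected missed events = n × p × (1 − s)
- Chance of at least one missed event = 1 − [1 − p(1 − s)]^n

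With p = 10%:

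| s | Expected reported rate | Missed events, n = 50 / 60 | Chance of at least one miss, n = 50 / 60 |
|---|---|---|---|
| 1.0 | 10% | 0 / 0 | 0% / 0% |
| 0.9 | 9% | 0.5 / 0.6 | 39.5% / 45.3% |
| 0.8 | 8% | 1.0 / 1.2 | 63.6% / 70.2% |
| 0.6 | 6% | 2.0 / 2.4 | 87.0% / 91.4% |

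Worked line for s = 0.8, n = 50: p(1 − s) = 0.10 × 0.20 = 0.02; 50 × 0.02 = 1.0; 1 − 0.98^50 = 0.636.

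Other pairs of assumptions: p = 5%, s = 0.9 gives a reported rate of 4.5% and 0.25 to 0.30 missed events; p = 20%, s = 0.6 gives 12% and 4.0 to 4.8. The table shows what under-reporting would do, not that it occurs.

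**The case against.** The strongest reply is that ascertainment here is active. Adverse events are assessed at every visit from the procedure onward. Laboratory tests and ECGs are scheduled, and neurological scales are to be done by a neurologist or neurology fellow where possible, otherwise by a certified team member. Investigator observation can include an abnormal result. Monitors verify that "All adverse events and device deficiencies are reported to Edwards without unjustified delay" and that "CRFs and queries are complete, recorded in a timely manner, and consistent with source documents"; the sponsor reviews eCRFs remotely, and "missing or unclear data will be requested as necessary throughout the trial". The sponsor may also obtain further medical documents (section 15) and reviews echo data throughout (section 20). An event found in any of these ways can be reported and then reviewed.

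Most of this stands, and it rules out several stronger readings:

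- A reader might infer that an unreported event can never be added. Nothing in the documents forbids it, and the routes above can bring one in.
- A reader might infer that the review strips out reported events, so that the net error must favour the device. The reviewer's stated tasks are seriousness, relatedness and classification; no section gives a power to remove events.
- A reader might infer that the core-lab haemodynamic results share the problem. Stenosis and regurgitation at 30 days are determined by the core lab without any adverse event report.

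It is also fair that the analysis is descriptive, with no performance goal for a complication rate to meet. Appendix A, the more detailed SAP announced in 8.5, the monitoring plan and the core-lab protocols are not in the supplied text and might contain triggers.

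What the reply does not supply is a step in the supplied text that sets the collected values against the endpoint definitions.

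**Conclusion.** The point holds as a gap in ascertainment. Medical review begins with reported events, and the supplied text describes no systematic screen of labs, ECGs and neurological scales, or of core-lab findings other than stenosis and regurgitation. Event-based secondary rates may be under-counted.

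It would go too far to say that these rates are biased down. The documents give no reporting sensitivity, full reporting would leave no bias, and the size cannot be estimated from the text. What can be stated is the weight of each miss, 1.7 to 2.0 points for n = 60 to 50, and its direction: a missed event can only lower the rate.

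The primary endpoint, all-cause death at 30 days, does not depend on this route. The conclusion assumes that no document outside the supplied text already sets data-driven triggers. This is a cheap improvement to secondary safety evidence, not a flaw in the primary analysis.

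**What to change.** Add to sections 7.1.3 and 13.3:

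1. Before each endpoint analysis, run a programmed listing of eCRF and core-lab values that meet the measurable part of the protocol's own endpoint definitions. It should cover creatinine, cardiac markers, hemoglobin, ECG conduction findings, NIHSS/mRS, and core-lab findings that bear on event-type endpoints such as valve thrombosis and mitral damage.
2. Send every flagged patient without a matching adverse event to the existing Medical Reviewer.
3. State that the reviewer may add an endpoint event.
4. State that endpoints are counted by the reviewer's classification, which also settles precedence among the three assessments in 13.3.

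If the separate SAP, Appendix A or the monitoring plan already contains such triggers, a cross-reference in both sections is sufficient.

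Cost: programming one listing from data already collected, and a few more cases for a reviewer already in place. The downside for the sponsor is that reported complication rates may rise.

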#### 1.1. Device Deficiency

Device deficiency is an inadequacy of a medical device with respect to its integrity, quality, durability, reliability, safety or performance. It includes malfunctions, user errors and inadequate labeling.

Device deficiencies include those deficiencies that did not lead to an adverse event but could have led to a medical occurrence:

- a. If intervention had not been made, or
- b. If circumstances had been less fortunate.

Reporting conventions for device deficiencies that could result in a Serious Adverse Event (SAE) are the same as those for an actual SAE.

### Device Deficiency and Vigilance Reporting

Device deficiencies which could have led to a serious adverse device effect should undergo the same reporting as serious adverse events. They should be reported to Edwards Lifesciences within 24 hours of awareness and to the EC and regulatory authorities as required by regulations or the EC.

Adverse device effects, device malfunctions and device failures must be reported to Edwards Lifesciences in accordance with the regulations and Edwards Lifesciences policies.

The Edwards Lifesciences 'Complaint Reporting Process' form is available in the site study document file.

## **14. Provisions on deviation from clinical trial protocol and correction of clinical trial protocol**

The investigator will not deviate from the protocol without the prior written approval of Edwards Lifesciences except in medical emergencies or in unforeseen, isolated instances where minor changes are made that will not increase the patient's risk or affect the validity of the trial. In medical emergencies, prior approval for protocol deviations will not be required, but the Edwards Lifesciences clinical research personnel must be notified within 24 hours of the incident.

All protocol deviations need to be recorded in the respective section of the eCRF and reported according national and ethics committee requirements. Periodic monitoring of protocol compliance will be performed for each site. The sponsor maintains the right to place a moratorium on enrollment in sites deemed to have excessive protocol compliance issues. A major protocol violation is the instance where a deviation significantly affects the integrity of the study and guidelines for Good Clinical Practice, such as when there is failure to obtain informed consent or violation of inclusion/exclusion criteria. In cases of major protocol violation, the principal investigator is required to make a written statement attesting to retraining or other action(s) to be

taken at his/her site to avoid such violations in the future.

## **15. Direct access to source data and files**

### Records

All records related to the study and qualifications of site personnel must be kept on file and available for review. These documents may include but are not limited to:

- Clinical trial investigational plan and all amendments, all approved versions
- Signed clinical trial agreement
- EC approval letter, including final informed consent
- EC membership list
- Correspondence relating to the trial
- CVs for all investigators and research coordinator
- Site personnel signature list
- Clinical monitor sign-in log
- Patient screening/enrollment log
- Lab certification and lab test normal ranges
- Reports (includes reports from investigator and sponsor)

All records related to the patients' consent and study data must be maintained for each patient enrolled in the trial. These records include and are not limited to:

- Signed Patient Informed Consent Form (latest approved site version)
- All completed eCRFs
- Supporting documentation of any complications and/or safety events.

Edwards Lifesciences requests that the investigator retain copies of procedure reports, procedure nursing notes and the results of any interventional procedures that occurs post trial procedure. Edwards Lifesciences reserves the right to secure data clarification and additional medical documentation on patients enrolled in this trial.

### Record Retention Policy

All clinical sites will maintain study records for a minimum of 15 years after marketing approval is obtained. After 15 years, clinical sites should follow hospital and regulatory guidelines for record retention. Record retention dates will be provided to all parties concerned by Edwards Lifesciences.

